 - Hematologic intolerance: Patients with grade 3 or 4 toxicity (absolute neutrophil count [ANC] or platelets) while on therapy that is recurrent after dose reduction to the lowest doses recommended by manufacturer
6. Eastern Cooperative Oncology Group (ECOG) performance status (PS) of 0, 1, or 2
7. Adequate end organ function as defined by (as per central laboratory tests):
 - Total bilirubin $\leq 1.5 \times$ ULN except for patients with Gilbert's syndrome who may only be included if total bilirubin $\leq 3.0 \times$ ULN or direct bilirubin $\leq 1.5 \times$ ULN

- Aspartate transaminase (AST) $\leq 3.0 \times \text{ULN}$
 - Alanine transaminase (ALT) $\leq 3.0 \times \text{ULN}$
 - Serum lipase $\leq 1.5 \times \text{ULN}$. For serum lipase $> \text{ULN} - \leq 1.5 \times \text{ULN}$, value must be considered not clinically significant and not associated with risk factors for acute pancreatitis
 - Alkaline phosphatase $\leq 2.5 \times \text{ULN}$
 - Creatinine clearance $\geq 50 \text{ mL/min}$ as calculated using Cockcroft-Gault formula
8. Patients must avoid consumption of grapefruit, Seville oranges or products containing the juice of each during the entire study and preferably 7 days before the first dose of study medications, due to potential CYP3A4 interaction with the study medications. Orange juice is allowed.
9. Written informed consent obtained prior to any screening procedures.
- 10a. Patients must have the following electrolyte values (as per central laboratory tests) within normal limits or corrected to be within normal limits with supplements prior to first dose of study medication:
- Potassium (potassium increase of up to 6.0 mmol/L is acceptable at study entry if associated with creatinine clearance within normal limits)
 - Total calcium (corrected for serum albumin); (calcium increase of up to 12.5 mg/dl or 3.1 mmol/L is acceptable at study entry if associated with creatinine clearance within normal limits)
 - Magnesium, with the exception of magnesium increase $> \text{ULN} - 3.0 \text{ mg/dL}$; $> \text{ULN} - 1.23 \text{ mmol/L}$ associated with creatinine clearance (calculated using Cockcroft-Gault formula) within normal limits.
11. Evidence of typical BCR-ABL1 transcript [e14a2 and/or e13a2] at the time of screening which are amenable to standardized RQ-PCR quantification.

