Isolated total Bilirubin elevation		
> ULN – 1.5 x ULN	Recommendation: Maintain dose level	Recommendation: Maintain dose level
> 1.5 - 3.0 x ULN	Recommendation: Hold dose. Monitor LFTs ^b weekly, or more frequently if clinically indicated, until resolved to ≤ 1.5 x ULN: if resolved in ≤ 14 days, then maintain dose level if resolved in > 14 days, then reduce dose ↓ 1 dose level	Recommendation: Hold dose. Monitor LFTs ^b weekly, or more frequently if clinically indicated, until resolved to ≤ 1.5 x ULN: if resolved in ≤ 14 days, then maintain dose level if resolved in > 14 days, then reduce dose ↓ 1 dose level
> 3.0 - 10.0 x ULN*	Mandatory: Hold dose. Monitor LFTs ^b weekly, or more frequently if clinically indicated, until resolved to ≤ 1.5 x ULN: if resolved in ≤ 14 days, then reduce dose ↓ 1 dose level if resolved in > 14 days, then discontinue patient from study drug treatment. The patient should be monitored weekly (including LFTs ^b), or more frequently if clinically indicated, until total bilirubin have resolved to baseline or stabilization over 4 weeks.	Mandatory: Hold dose. Monitor LFTs ^b weekly, or more frequently if clinically indicated, until resolved to ≤ 1.5 x ULN: if resolved in ≤ 14 days, then reduce dose ↓ 1 dose level if resolved in > 14 days, then discontinue patient from study drug treatment. The patient should be monitored weekly (including LFTs ^b), or more frequently if clinically indicated, until total bilirubin have resolved to baseline or stabilization over 4 weeks.
> 10.0 x ULN*	Mandatory: Permanently discontinue patient from study drug treatment. The patient should be monitored weekly (including LFTs ^b), or more frequently if clinically indicated, until total bilirubin have resolved to baseline or stabilization over 4 weeks.	Mandatory: Permanently discontinue patient from study drug treatment. The patient should be monitored weekly (including LFTs ^b), or more frequently if clinically indicated, until total bilirubin have resolved to baseline or stabilization over 4 weeks.
Isolated AST or ALT elevation		
> ULN - 3.0 x ULN	Recommendation: Maintain dose level	Recommendation: Maintain dose level

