> 3.0 - 5.0 x ULN	Recommendation: Maintain dose level. Repeat LFTs ^b as soon as possible, preferably within 48-72 hours from awareness of the abnormal results; if abnormal lab values are confirmed upon the repeat test, then monitor LFTs ^b weekly, or more frequently if clinically indicated, until resolved to ≤ 3.0 x ULN	Recommendation: Maintain dose level. Repeat LFTs ^b as soon as possible, preferably within 48-72 hours from awareness of the abnormal results; if abnormal lab values are confirmed upon the repeat test, then monitor LFTs ^b weekly, or more frequently if clinically indicated, until resolved to ≤ 3.0 x ULN

[figure not shown]
Dose modifications for both asciminib and bosutinib Please note that if a patient requires a dose interruption of > 28 days for each toxicity, then the patient must be discontinued from the study treatment		
Worst toxicity CTCAE Grade 4.03	Asciminib	Bosutinib
> 5.0 - 10.0 x ULN	Mandatory: Hold dose. Repeat LFTs ^b as soon as possible, preferably within 48-72 hours from awareness of the abnormal results; monitor LFTs ^b weekly, or more frequently if clinically indicated, until resolved to ≤ 3.0 x ULN: Then If resolved in ≤ 14 days, maintain dose level If resolved in > 14 days, reduce dose ↓ 1 dose level	Mandatory: Hold dose. Repeat LFTs ^b as soon as possible, preferably within 48-72 hours from awareness of the abnormal results; monitor LFTs ^b weekly, or more frequently if clinically indicated, until resolved to ≤ 2.5 x ULN: Then Recommendation: If resolved in ≤ 28 days, reduce dose ↓ 1 dose level Recommendation: If resolved in > 28 days, Discontinue patient from study drug treatment
> 10.0 - 20.0 x ULN	Mandatory: Hold dose. Repeat LFTs ^b as soon as possible, preferably within 48-72 hours from awareness of the abnormal results; monitor LFTs ^b weekly, or more frequently if clinically indicated, until resolved to ≤ baseline. Then reduce dose ↓ 1 dose level.	Mandatory: Hold dose. Repeat LFTs ^b as soon as possible, preferably within 48-72 hours from awareness of the abnormal results; monitor LFTs ^b weekly, or more frequently if clinically indicated, until resolved to ≤ 2.5 x ULN. Then Recommendation: If resolved in ≤ 28 days, reduce dose ↓ 1 dose level maintain dose level Recommendation: If resolved in > 28 days, Discontinue patient from study drug treatment.

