> 20.0 x ULN	Mandatory: Hold dose. Repeat LFTs ^b as soon as possible, preferably within 48-72 hours from awareness of the abnormal results; monitor LFTs ^b weekly, or more frequently if clinically indicated, until resolved to ≤ 3 x ULN (or ≤ 5 x ULN for patients with baseline value > 3.0 -5.0 x ULN), then resume treatment at reduce dose ↓ 1 dose level. Only 1 dose reduction is allowed; if reoccurs at > 5 x ULN, discontinue patient from study drug treatment.	Mandatory: Hold dose. Repeat LFTs ^b as soon as possible, preferably within 48-72 hours from awareness of the abnormal results; monitor LFTs ^b weekly, or more frequently if clinically indicated, until resolved to ≤ 2.5 x ULN (then Recommendation: If resolved in ≤ 28 days, reduce dose ↓ 1 dose level maintain dose level Recommendation: If resolved in > 28 days, Discontinue patient from study drug treatment

[figure not shown]
Dose modifications for both asciminib and bosutinib Please note that if a patient requires a dose interruption of > 28 days for each toxicity, then the patient must be discontinued from the study treatment		
Worst toxicity CTCAE Grade 4.03	Asciminib	Bosutinib
Combined ^c elevations of AST or ALT and total bilirubin		
For patients with normal baseline ALT and AST and total bilirubin value: AST or ALT >3.0 x ULN combined with total bilirubin >2.0 x ULN without evidence of cholestasis ^d For patients with elevated baseline AST or ALT or total bilirubin value [AST or ALT >2 x baseline AND > 3.0 x ULN]	Mandatory: Permanently discontinue patient from study drug treatment. Repeat as soon as possible, preferably within 48 hours from awareness of the abnormal results, then with weekly monitoring of LFTs ^b), or more frequently if clinically indicated, until AST, ALT, or bilirubin have resolved to baseline or stabilization over 4 weeks. Refer to Section 6.3.3.1 for additional follow-up evaluations as applicable.	Mandatory: Permanently discontinue patient from study drug treatment. Repeat as soon as possible, preferably within 48 hours from awareness of the abnormal results, then with weekly monitoring of LFTs ^b), or more frequently if clinically indicated, until AST, ALT, or bilirubin have resolved to baseline or stabilization over 4 weeks. Refer to Section 6.3.3.1 for additional follow-up evaluations as applicable.
Investigation (metabolic)		
Asymptomatic amylase and/or lipase elevation		

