Dose modifications for both asciminib and bosutinib		
Please note that if a patient requires a dose interruption of > 28 days for each toxicity, then the patient must be discontinued from the study treatment		
Worst toxicity CTCAE Grade 4.03	Asciminib	Bosutinib

If combined elevations of AST or ALT and total bilirubin do not meet the defined thresholds, please follow the instructions for isolated elevation of total bilirubin and isolated elevation of AST/ALT, and take a conservative action based on the degree of the elevations (e.g. discontinue treatment at the situation when hold dose is needed for one parameter and discontinue treatment is required for another parameter). After all elevations resolve to the defined thresholds that allow treatment re-initiation, re-start the treatment either at the same dose or at one dose lower if meeting a criterion for dose reduction
 
^d “Cholestasis” defined as ALP elevation (>2.0 x ULN and R value <2) in patients without bone metastasis, or elevation of ALP liver fraction in patients with bone metastasis
 
Note: The R value is calculated by dividing the ALT by the ALP, using multiples of the ULN for both values. It denotes whether the relative pattern of ALT and/or ALP elevation is due to cholestatic (R ≤ 2), hepatocellular (R ≥ 5), or mixed (R >2 and < 5) liver injury
 
* Note: If total bilirubin > 3.0 x ULN is due to the indirect (non-conjugated) component only, and hemolysis as the etiology has been ruled out as per institutional guidelines (e.g., review of peripheral blood smear and haptoglobin determination), then ↓ 1 dose level and continue treatment at the discretion of the investigator.
 
** Note: A CT scan or other imaging study to assess the pancreas, liver, and gallbladder must be performed within 1 week of the first occurrence of any ≥ Grade 3 of amylase and/or lipase. If asymptomatic Grade 2 elevations of lipase and/or amylase occur again at the reduced dose, patients will be discontinued permanently from study treatment.
 
*** Note: antidiarrheal medication is recommended at the first sign of abdominal cramping, loose stools or overt diarrhea
		

[figure not shown]

Table 6-3 Dose reduction steps for asciminib and bosutinib

Dose reduction*			
	Starting dose level – 0	Dose level – 1	
Asciminib BID	40 mg tablet BID (total daily dose 80 mg)	20 mg tablet BID (total daily dose 40 mg)	
*Dose reduction should be based on the worst toxicity demonstrated at the last dose.			

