6.3.3.1 Follow up on potential drug-induced liver injury (DILI) cases

Patients with transaminase increase combined with TBIL increase may be indicative of potential DILI, and should be considered as clinically important events.

The threshold for potential DILI may depend on the patient's baseline AST/ALT and TBIL value; patients meeting any of the following criteria will require further follow-up as outlined below:

- For patients with normal ALT and AST and TBIL value at baseline: AST or ALT > 3.0 x ULN combined with TBIL > 2.0 x ULN
- For patients with elevated AST or ALT or TBIL value at baseline: [AST or ALT > 2 x baseline AND > 3.0 x ULN] OR [AST or ALT > 8.0 x ULN], combined with [TBIL > 2 x baseline AND > 2.0 x ULN]

Medical review needs to ensure that liver test elevations are not caused by cholestasis, defined as ALP elevation > 2.0 x ULN with R value < 2 in patients without bone metastasis, or elevation of ALP liver fraction in patients with bone metastasis.

Note: (The R value is calculated by dividing the ALT by the ALP, using multiples of the ULN for both values. It denotes whether the relative pattern of ALT and/or ALP elevation is due to cholestatic ($R \leq 2$), hepatocellular ($R \geq 5$), or mixed ($R > 2$ and < 5) liver injury).

In the absence of cholestasis, these patients should be immediately discontinued from study drug treatment, and repeat LFT testing as soon as possible, preferably within 48 hours from the awareness of the abnormal results. The evaluation should include laboratory tests, detailed history, physical assessment and the possibility of liver metastasis or new liver lesions, obstructions/compressions, etc.

1. Laboratory tests should include ALT, AST, albumin, creatinine kinase, total bilirubin, direct and indirect bilirubin, GGT, prothrombin time (PT)/INR and alkaline phosphatase.
2. A detailed history, including relevant information, such as review of ethanol, concomitant medications, herbal remedies, supplement consumption, history of any pre-existing liver conditions or risk factors, should be collected.
3. Further testing for acute hepatitis A, B, C or E infection and liver imaging (e.g. biliary tract) may be warranted.

4. Obtain PK sample, as close as possible to last dose of study drug, if PK analysis is performed in the study.

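### The cholestasis exemption from the liver stopping rule ignores baseline ALP, so a stable entry ALP above 2.0 and up to 2.5 x ULN can waive the mandatory permanent stop

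*Combined protocol and SAP*

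**What the plan says.** All values below are multiples of the upper limit of normal, and all references are to the protocol at Amendment 3.

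For patients with normal baseline ALT, AST and bilirubin, the combined-elevation row of Table 6-2 (Section 6.3.1) requires permanent discontinuation in both arms for "AST or ALT >3.0 x ULN combined with total bilirubin >2.0 x ULN without evidence of cholestasis". Footnote d gives cholestasis as "defined as ALP elevation (>2.0 x ULN and R value <2) in patients without bone metastasis". Section 6.3.3.1 repeats the definition and gives it to the medical reviewer: "Medical review needs to ensure that liver test elevations are not caused by cholestasis, defined as ALP elevation" above 2.0 with R below 2. It ties immediate discontinuation to cholestasis being absent. R is ALT divided by ALP; AST does not enter.

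Inclusion criterion 7 (Section 5.2) allows ALP up to 2.5 at entry. Section 6.3.3.1 has a baseline-adjusted branch for ALT, AST and bilirubin but none for ALP.

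Footnote c sends cases to the isolated rows "If combined elevations of AST or ALT and total bilirubin do not meet the defined thresholds", and asks for the conservative action when two rows differ. Footnote b has ALP isoforms measured once ALP exceeds 2.0, and direct and indirect bilirubin once total bilirubin exceeds 2.0.

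**The concern.** The exemption is meant to separate a cholestatic picture from a hepatocellular one. That works if ALP above 2.0 is a new finding. Where it was present at screening, the ALP half of the exemption is already met on day 1 and says nothing about the new event.

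ALP is the exception among the liver tests used here. The entry limit for ALT and AST (3.0) does not exceed their trigger (> 3.0). The usual entry limit for bilirubin (1.5) is below its trigger (> 2.0), and patients with Gilbert's syndrome who enter higher fall into the baseline-adjusted branch. Only ALP has an entry limit (2.5) above its decision threshold (> 2.0) with no adjustment.

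At stake is the bar on rechallenge after a possible drug-induced liver injury, which Section 6.3.3.1 treats as a clinically important event.

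**Working it through.** **Inputs.** ALP entry limit: <= 2.5 (Section 5.2, criterion 7). Trigger at normal baseline: ALT or AST > 3.0 with bilirubin > 2.0 (Table 6-2; Section 6.3.3.1). Exemption: ALP > 2.0 and R < 2 (footnote d; Section 6.3.3.1). R = ALT / ALP.

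**Exempt range.** Hold ALP at its entry value b. R < 2 is the same as ALT < 2b, so for b > 2.0 the exempt ALT range is 3.0 < ALT < 2b.

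| Stable ALP b | 2b | Exempt ALT, with bilirubin > 2 |
|---|---|---|
| 2.00 | 4.00 | none (ALP is not > 2.0) |
| 2.01 | 4.02 | > 3.0 to < 4.02 |
| 2.1 | 4.2 | > 3.0 to < 4.2 |
| 2.3 | 4.6 | > 3.0 to < 4.6 |
| 2.5 | 5.0 | > 3.0 to < 5.0 |

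Because R ignores AST, AST > 3 with ALT < 2b is exempt as well.

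**Cases.**
- ALP 2.3 unchanged, ALT 4.5, bilirubin 2.5: R = 4.5 / 2.3 = 1.96. The definition is met and the case is exempt.
- ALP 2.3 unchanged, ALT 2.5, AST 4.5, bilirubin 2.5: R = 2.5 / 2.3 = 1.09. Exempt.
- ALP 2.5 unchanged, ALT 5.0, bilirubin 2.5: R = 5.0 / 2.5 = 2.0. Not exempt, so the stop applies.

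**What governs an exempted case.** Footnote c covers combined rises below the thresholds. These cases exceed both numeric thresholds, so using the isolated rows is an inference. On that reading:

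| Finding | Isolated row of Table 6-2 |
|---|---|
| ALT or AST > 3 to 5 | "Recommendation: Maintain dose level. Repeat LFTs" |
| AST > 5 to 10 | "Mandatory: Hold dose. Repeat LFTs" |
| Bilirubin > 2 to 3 | Recommended hold, weekly liver tests, then "if resolved in ≤ 14 days, then maintain dose level if resolved in > 14 days, then reduce dose ↓ 1 dose level" |
| Bilirubin > 3 to 10 | Mandatory hold; one level lower if resolved in <= 14 days, discontinue if later |
| Bilirubin > 10 | Mandatory permanent stop |

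The last two rows are subject to the note on purely indirect bilirubin with hemolysis ruled out. Every exempted case has bilirubin > 2, so under the conservative-action instruction the bilirubin hold overrides the instruction to maintain dose. With stable ALP, an exempt ALT is always below 5.0; only AST can reach the higher transaminase rows.

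**Residual.** With bilirubin > 2 to 3 and ALT and AST both <= 5, no isolated row mandates anything. The permanent stop becomes a recommended hold, followed by restart at the same dose or one level lower.

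**The case against.** The best reply is that the exemption is not automatic. Section 6.3.3.1 asks medical review whether the rises are caused by cholestasis, and an ALP unchanged since screening does not naturally explain a new ALT and bilirubin rise. The reviewer has the screening value, the isoforms and the bilirubin fractions. This has force, and a careful reviewer may well reach the right answer. But the definition supplied for patients without bone metastasis uses none of that information, so the text supports the wrong answer as readily as the right one.

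The second reply is that much protection remains. This stands. Besides the isolated rows, Table 6-2 has a general row for non-hematologic reactions. For asciminib it recommends a hold at grade 2, mandates a hold and dose reduction at grade 3, and mandates a permanent stop at grade 4; for bosutinib it is more lenient. Section 6.3.1 requires discontinuation after an interruption of more than 28 days, or if the toxicity recurs after restart at a lower dose. Section 6.3.3.1 requires follow-up of every case meeting the laboratory criteria; only the immediate stop depends on cholestasis.

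A reader might infer more than the documents support:
- That such a patient simply continues at full dose. The bilirubin hold governs.
- That no instruction reaches the case. The rules above do, though none restores the permanent stop in the residual range.
- That these cases escape serious adverse event reporting because cholestasis counts as an alternative cause. The text does not say so.
- That Table 6-2 has the same gap for patients with elevated baseline ALT, AST or bilirubin. Its row for them prints no cholestasis exemption.

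**Conclusion.** The point holds as a gap in the written rule, at low severity. With normal baseline ALT, AST and bilirubin and a stable ALP b (2.0 < b <= 2.5), a new ALT > 3 to < 2b, or AST > 3 with ALT < 2b, together with bilirubin > 2 meets the cholestasis definition although ALP has not changed. The practical loss is mainly confined to bilirubin > 2 to 3 with ALT and AST <= 5.

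This assumes that the reviewer applies the definition as printed and that exempted cases are handled through the isolated rows. The documents give neither the share of patients entering with ALP > 2.0 to 2.5 nor the rate of combined rises. Exclusion criterion 9 removes patients with a history of liver disease, and several conditions must coincide among 222 patients. The number affected is unknown and probably very small.

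**What to change.** Add to Table 6-2 footnote d and to Section 6.3.3.1: *In patients whose baseline ALP is already > 2.0 x ULN, an ALP that has not risen from baseline does not by itself qualify as cholestasis and does not exempt the case from permanent discontinuation; medical review should compare with baseline ALP and use the ALP isoforms and bilirubin fractions already obtained.*

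The stable-ALP cases above would then keep the mandatory stop. The cost is one sentence in two places, with no new data. Section 6.3.3.1 uses one definition for both baseline groups, so the sentence there would reach both. The downside is that a rare patient with true cholestasis and an unchanged high baseline ALP would be stopped, which matters because Section 2.2 describes limited options outside the study for patients failing bosutinib.

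A numeric rise factor should be left to the sponsor's hepatic safety experts. A rule such as ALP > 1.5 x baseline has no source in the documents and would alter the exemption for every baseline above 2.0 / 1.5 = 1.33. It would also stop some patients with a real rise, such as 2.3 to 3.2 (3.2 / 2.3 = 1.39) or 1.8 to 2.5 (2.5 / 1.8 = 1.39). In its favor, it would catch a drift across the threshold that the sentence above misses: ALP 1.95 to 2.05 with ALT 4.0 gives R = 4.0 / 2.05 = 1.95, still exempt. That trade-off is clinical.

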6.3.4 Anticipated risks and safety concerns of the study drug

Appropriate eligibility criteria, as well as specific dose modification and stopping rules are included in this protocol. Recommended guidelines for prophylactic or supportive treatment for expected toxicities, including management of study-drug induced adverse events, i.e., hyperglycemia, skin toxicity and diarrhea are provided in [Table 6-2](#). Refer to preclinical toxicity and or clinical data found in the [[Asciminib Investigator’s Brochure](#)] or bosutinib label.

6.4 Concomitant medications for patients on asciminib

The patient must be told to notify the investigational site about any new medications he/she takes after the start of the study drug. All medications (other than study drug and including over-the-counter treatment and nutritional or vitamin supplements) and significant non-drug therapies (including physical therapy, herbal/natural medications and blood transfusions) administered during the study must be listed on the “Concomitant Medications/Significant non-drug therapies” section of the eCRF.

Chronic medication should be maintained at the same dose and schedule throughout the study period, as medically feasible.

[figure not shown]
All prior antineoplastic surgery, chemotherapy, biologic, immunologic and radiation therapy must be recorded in the “Prior antineoplastic therapy” section of the eCRF.

In general, concomitant medications and therapies deemed necessary for the supportive care and safety of the patient are allowed, provided their use is documented in the patient records and on the appropriate case report form, including the medication’s duration (start and end dates or if continuing at final exam). These include blood and platelet transfusions for patients with anemia and with thrombocytopenia.

